7. STUDY DESIGN

This is a phase III, two-arm, matched-pair, cluster randomized trial. The study will be conducted at 16 sites across India (8 PWID and 8 MSM). Eligible, HIV-positive PWID or MSM will be recruited at each site prior to randomization. In each site pair, one site will be assigned to the control condition and the other site to the incentive intervention.

1. Control condition – Free-of-charge HIV care and ART available at government HIV clinics. ICCs provide HIV counseling, risk reduction services, and peer outreach to support HIV treatment linkage, adherence and retention.
2. Incentive intervention – Control condition services plus ICCs offer HIV treatment incentives (non-cash vouchers for goods) for completing verifiable HIV care activities.

In addition to the quantitative endpoints from the trial, we will also collect mixed methods data to understand how treatment incentives were perceived by different stakeholders. During the latter part of the intervention phase, we will conduct an epidemiologic survey among PWID and MSM at all study sites using RDS. The survey will provide insight into the community-level impact of the intervention and to trends in HIV testing, prevention, and treatment (by comparing with results of 2 prior surveys). Finally, a cost-effectiveness evaluation will be conducted.

The study duration will be approximately 48 months. Ethnography and preparatory work at the sites will take 6 months. Participants will be enrolled over 12 months and then followed for a 24-month intervention phase. Finally, an epidemiologic survey will be conducted at all sites at the conclusion of the intervention phase that will extend another 6 months.

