8. STUDY POPULATION

We will recruit cohorts of HIV-positive participants at each ICC site, with roll-out of the study arm allocation (incentive intervention or control condition) after or near the conclusion of cohort

enrollment. Cohort participants will be followed for 24 months during the intervention phase in order to accomplish primary and secondary objectives. The exploratory objectives require i) collecting of mixed methods data on HIV care incentives from key stakeholders, ii) conducting an RDS survey at each site targeting either PWID or MSM, depending on the site, and iii) conducting cost-effectiveness analyses.

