13.2.2 Secondary Endpoints

- Survival with suppressed viral load at 6, 18, and 24 months.
- Proportion with at least one suppressed viral load during study follow-up (6, 12, 18, or 24 months).
- Time to ART initiation, recorded from government HIV treatment records, among cohort participants that were ART-naïve at baseline.
- Retention to HIV care during follow-up, defined as having 1 or more visits to a government ART clinic in each 6-month period of study follow-up.
- ART possession ratio (a measure of medication adherence), defined as the time in possession of ART divided by the follow-up time. Follow-up time will commence at enrollment for ART-experienced participants and at ART initiation for ART-naïve participants. Follow-up time will be censored at the end of trial follow-up, death, or loss-to-follow-up. The amount of time in possession of ART will be determined from ART dispensation logs maintained by government HIV clinics.
- Mortality, defined as a report of a participant's death from a family member or a close

friend. Death records are not maintained by local, state, or national governments in India.

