13.2.3 Exploratory Endpoints

- Rate of HIV testing in ICCs, defined as number of HIV tests performed in an ICC per unit time. This is an ICC-level endpoint. The number of HIV tests and the testing results are recorded in a computerized ICC database. For each matched site pair, follow-up will commence on the date that the intervention is rolled-out at the intervention site in the pair. Follow-up will end at the conclusion of the active intervention period.
- New HIV diagnosis rate in ICCs, defined as the number of persons testing newly HIV-positive in the ICC per unit time. This is an ICC-level endpoint. For each matched site pair, follow-up will commence on the date that the intervention is rolled-out at the intervention site in the pair. Follow-up will end at the conclusion of the active intervention period.
- Mixed methods evaluation of treatment incentives obtained by i) survey questions of cohort participants at the final (24-month) study visit (quantitative component), and ii) IDIs with ICC clients and ICC staff (qualitative component).
- Community-level effects will be assessed by an end-of-study RDS survey among PWID or MSM (according to site). RDS is a network-based sampling method, in which participants recruit people from their social networks with a coupon tracking system. Sampling weights are generated that provide unbiased estimates of characteristics of interest in the underlying population. Our team has experience using RDS to assess the community-level impact of a structural intervention (1). In this trial, we will use RDS estimates to 1) assess for community-level impact of the incentive intervention compared with the control condition, and 2) to assess epidemiologic trends in HIV prevention, care continuum, HIV prevalence, and HIV incidence by comparison with prior surveys conducted in these cities. Endpoints to be assessed in the RDS survey include:
 - Recent HIV testing, defined as the proportion that self-report HIV testing in the prior 12 months among all survey participants, except those who are aware of their HIV-positive status and report diagnosis more than 12 month previously.
 - Awareness of HIV-positive status, defined as the proportion that self-report HIV-positive status in interview among participants subsequently determined to be HIV seropositive.
 - Recent HIV care visit, defined as the proportion of HIV-positive participants who report a visit with an HIV care provider in the prior 6 months.

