13.6 Randomization and Masking Procedures

In cluster-randomized trials with a relatively low number of sites (clusters), substantial imbalances between study arms can emerge easily by chance. To reduce the likelihood of large study arm imbalances for key variables, we restricted the pool of potential allocation combinations by removing combinations with large baseline imbalances. With no restrictions, there were a total of 16 potential allocations (i.e., 4^2) within each stratum (PWID/MSM), or 256 overall allocations. First, to reduce large imbalances within the strata, randomization allocations were dropped ($n=8$, 4 in each stratum) due to imbalances in prevalence of viremic persons or viral suppression (i.e., all sites with higher/lower prevalence were allocated to one arm). This resulted in 12 allocations for each stratum. These allocations crossed (PWID x MSM), resulted in 144 potential allocations (i.e., 12^2). Then, an additional overall restriction was placed in which allocations were dropped ($n=36$) due to imbalances in prevalence of viremic persons or viral suppression (i.e., higher/lower prevalence 6:2 pair ratio in different arms). This resulted in a total of 108 potential allocations. We checked across all these potential allocations for sites that either always or never appeared in the same study arm. No sites always or never appeared in the same

arm - with the exception matched sites, which, by definition, never appeared in the same arm.

Of the 108 allocation combinations that remained after site pairing and restriction, one allocation was selected in a ball drawing ceremony on January 3, 2018 that was refereed by two statisticians who were independent of the study. The ceremony was video recorded and is available at <https://youtu.be/UmXBG2CluNA>. Because of the cluster randomized design, masking participants or research staff was not feasible. However, the randomization team withheld the randomization results for each site pair until cohort recruitment was complete or nearly complete at both sites in the pair. The implementation teams in India recruited cohorts at each site without knowing whether the site would be intervention or control.

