13.9.2 Secondary outcomes

Secondary binary outcomes including i) survival with suppressed viral load at other time points (6, 18, and 24 months), ii) proportion with at least one suppressed viral load during follow-up, iii) proportion retained to HIV care (defined as the proportion with at least one visit to the ART center per 6-month follow-up interval), and iv) mortality will be analyzed similarly resulting in pair-wise differences in proportions with a two-stage procedure for confounder adjustment, if appropriate (criteria for confounders outlined in prior section).

For two other secondary outcomes, we will use similar pair-matched cluster approaches with a two-stage procedure for confounder adjustment. First, we will compare risk of initiating ART at intervention vs. control sites (among the subset that is ART-naïve at baseline) using a Cox proportional hazards model. Second, we will compare ART possession ratio (defined as number of days covered by ART dispensations divided by the number of days under observation) by calculating a mean difference between intervention and control conditions.

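### The ART possession ratio counts time on ART before incentives are rolled out at the pair, mainly in ART-experienced participants, which modestly dilutes the between-arm difference

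*Combined protocol and SAP*

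**What the plan says.** Section 13.2.2 defines the possession ratio as time in possession of ART over follow-up time, and fixes the start of that time: "Follow-up time will commence at enrollment for ART-experienced participants and at ART initiation for ART-naïve participants". The clock ends at the end of trial follow-up, death or loss. Section 13.9.2 restates the ratio as "defined as number of days covered by ART dispensations divided by the number of days under observation" and gives no other start. It compares the arms by one mean difference covering ART-experienced and ART-naïve participants together.

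The intervention starts later. Section 8 describes recruiting the cohorts "with roll-out of the study arm allocation (incentive intervention or control condition) after or near the conclusion of cohort" enrolment. Section 13.6 says that "one allocation was selected in a ball drawing ceremony on January 3, 2018", and that the randomization team "withheld the randomization results for each site pair until cohort recruitment was complete or nearly complete at both sites in the pair".

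For the two ICC-level exploratory rates, section 13.2.3 uses a different origin: "follow-up will commence on the date that the intervention is rolled-out at the intervention site in the pair".

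**The concern.** Someone already on ART who enrols before the pair's roll-out contributes days to both numerator and denominator while neither site of the pair offers incentives. The intervention cannot change possession on those days. Averaging them in shrinks the expected difference in proportion to their share of follow-up. ART-naïve participants who start ART before roll-out do the same, but only from their start date.

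Some pre-roll-out time is very likely. Allocation was held back pair by pair until recruitment was complete or nearly so, so most of each cohort should have enrolled before release. The trial-wide dates agree. The draw was on 3 January 2018 and enrolment ended in October 2018 (section 13.1). If enrolment took the 12 months planned in section 7, it began about October or November 2017, before any allocation existed.

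At stake is the estimate for one secondary endpoint. It matters because timely refills carry the largest maximum incentive in Table 2 (INR 3600), and a ratio built from dispensations is the outcome closest to that behaviour.

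**Working it through.** The plan gives no sample size or effect size for the possession ratio, so there is no figure to reproduce. Its only sample-size result, 8 pairs, concerns viral suppression and is unaffected.

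**Model.** Let f be the share of counted follow-up that precedes roll-out, and δ the effect on possession after roll-out. The expected difference is (1 − f) × δ.

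**Assumptions.** None of these is in the documents. Enrolment is uniform over T = 3 or 6 months within a pair, roll-out falls at the end of recruitment, and 24 months are counted from enrolment.

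**ART-experienced participants.** The mean lag to roll-out is T/2, so f = T/48.
- T = 3: f = 6.25%, and 10 points becomes 9.4.
- T = 6: f = 12.5%, and 10 points becomes 8.8.

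Variants:
- Roll-out at 90% of recruitment: mean lag = (0.9T)²/(2T) = 0.405T, so f = 0.405T/24 = 5.1% / 10.1%, showing as 9.5 / 9.0 points.
- A pair that finished in October 2018 and was cut off 17 months later, in March 2020: f = 1 − (17/T) ln((17 + T)/17) = 7.9% / 14.4%, showing as 9.2 / 8.6 points.
- The 24 months counted after roll-out instead: with lag W, f = W/(24 + W), mean 5.8% / 10.7%. Dilution remains on either reading.

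**ART-naïve participants who start ART.** For start time S, lag W and follow-up F, the share is (W − S)/(F − S) when S < W, and zero otherwise. This never exceeds W/F, the share of an ART-experienced participant with the same W and F. I simulated exponential start times with assumed control hazards of 0.03 to 0.10 per month, and a hazard ratio of 1 before roll-out and 2.33 after (the pilot figure in section 5.1). The mean share is 0.2-0.7% for T = 3 and 1.0-2.5% for T = 6. Faster starts raise it: with T = 6 and a median start of 3 months or 1 month in both arms, it is 4.5% or 8.2%.

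**Whole endpoint.** Assume that half of those counted are ART-experienced, with the slower hazards above.
- T = 3: from (6.25 + 0.24)/2 = 3.2% to (6.25 + 0.66)/2 = 3.5%; 10 points becomes about 9.7.
- T = 6: from (12.5 + 0.97)/2 = 6.7% to (12.5 + 2.54)/2 = 7.5%; 10 points becomes about 9.3.

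**Power.** Assume 8 pairs, a paired t-test with 7 df and 80% power without dilution. Let pre- and post-roll-out pair differences have equal variance and correlation r. The noncentrality is multiplied by (1 − f)/√[(1 − f)² + f² + 2r f(1 − f)].

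| f | r = 1 | r = 0.5 | r = 0 |
|---|---|---|---|
| 6.25% | 75% | 77% | 80% |
| 12.5% | 69% | 74% | 79% |

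The 12.5% row applies only if everyone counted is ART-experienced.

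**The case against.** The strongest reply is that an enrolment clock is a coherent and conservative choice for endpoints on individuals who have an enrolment date. The rates in section 13.2.3 are counts per ICC with no individual origin, so a calendar roll-out date is natural there and sets no binding precedent. Restarting the clock drops participants who die or are lost before roll-out. It would also redefine a written endpoint, toward a larger effect, in an unmasked trial whose follow-up was already suspended when version 2.0 was written. All of this stands. It limits how the remedy should be used, but does not remove the dilution.

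A reader might infer more than the documents support:
- **A contradiction with section 13.2.3.** The two sections govern different kinds of endpoint. Section 13.2.3 shows only that the pair roll-out dates are needed anyway.
- **Dilution of 19-25% and power of 56-63%.** These need 12 months of accrual within a pair, only ART-experienced participants, and a standard error that does not change with f. The 12 months in section 7 are trial-wide, while allocation was released pair by pair, and no pair is said to have taken that long.
- **9.4 / 8.8 points as the result for the endpoint.** Those figures hold for ART-experienced participants alone, whereas section 13.9.2 pools both groups.
- **A false-positive risk, or a problem with the primary analysis.** Recruitment teams did not know the allocation, so pre-roll-out time should be alike between arms in expectation. The primary endpoint is viral suppression at the 12-month visit, not accumulated time.

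Section 8 also says "Cohort participants will be followed for 24 months during the intervention phase", which sits awkwardly with visits counted from baseline. That wording deserves clarification but adds no weight here.

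**Conclusion.** The point holds as a modest, conservative attenuation of one secondary endpoint. Mechanism and direction follow from sections 8, 13.2.2 and 13.6, and no other section removes the pre-roll-out time.

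The size cannot be fixed from the documents. Under the stated assumptions, the whole endpoint loses about 3-4% of its effect with 3-month pair accrual and about 7% with 6-month accrual. It would lose more with a larger ART-experienced share, quicker ART starts or longer accrual, and less if pairs recruited quickly. Any loss of power depends on a correlation that is not stated, and may be negligible.

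**What to change.** In sections 13.2.2 and 13.9.2, add a dated, pre-specified analysis of the possession ratio. Start the clock at the later of the pair's roll-out date and enrolment (ART-experienced) or ART initiation (ART-naïve), identically at both sites of the pair. Make it the main definition only if no possession data by arm have been seen. Otherwise keep it as a sensitivity analysis beside the enrolment-clock version. State in section 13.9.2 when the days under observation begin.

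Report the number who die or are lost before roll-out by arm, and the months from enrolment to roll-out by pair. The second figure will show how much dilution there really was.

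The cost is SAP wording and re-derivation. The roll-out dates are already needed for section 13.2.3, and Appendix I schedules abstraction of ART-book data at screening and every follow-up visit. The downside is slightly less observation time per person and the exclusion of those lost before roll-out. Similar sensitivity analyses for ART initiation and the 6-month retention periods are optional.

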13.2.3 Exploratory Endpoints

- Rate of HIV testing in ICCs, defined as number of HIV tests performed in an ICC per unit time. This is an ICC-level endpoint. The number of HIV tests and the testing results are recorded in a computerized ICC database. For each matched site pair, follow-up will commence on the date that the intervention is rolled-out at the intervention site in the pair. Follow-up will end at the conclusion of the active intervention period.
- New HIV diagnosis rate in ICCs, defined as the number of persons testing newly HIV-positive in the ICC per unit time. This is an ICC-level endpoint. For each matched site pair, follow-up will commence on the date that the intervention is rolled-out at the intervention site in the pair. Follow-up will end at the conclusion of the active intervention period.
- Mixed methods evaluation of treatment incentives obtained by i) survey questions of cohort participants at the final (24-month) study visit (quantitative component), and ii) IDIs with ICC clients and ICC staff (qualitative component).
- Community-level effects will be assessed by an end-of-study RDS survey among PWID or MSM (according to site). RDS is a network-based sampling method, in which participants recruit people from their social networks with a coupon tracking system. Sampling weights are generated that provide unbiased estimates of characteristics of interest in the underlying population. Our team has experience using RDS to assess the community-level impact of a structural intervention (1). In this trial, we will use RDS estimates to 1) assess for community-level impact of the incentive intervention compared with the control condition, and 2) to assess epidemiologic trends in HIV prevention, care continuum, HIV prevalence, and HIV incidence by comparison with prior surveys conducted in these cities. Endpoints to be assessed in the RDS survey include:
 - Recent HIV testing, defined as the proportion that self-report HIV testing in the prior 12 months among all survey participants, except those who are aware of their HIV-positive status and report diagnosis more than 12 month previously.
 - Awareness of HIV-positive status, defined as the proportion that self-report HIV-positive status in interview among participants subsequently determined to be HIV seropositive.
 - Recent HIV care visit, defined as the proportion of HIV-positive participants who report a visit with an HIV care provider in the prior 6 months.
 - Current ART use, defined as the proportion of HIV-positive participants who report ART use in the prior 30 days.
 - HIV RNA suppression, defined as the proportion of HIV-positive participants with measured HIV RNA <150 copies/mL
 - Prevalence of viremic individuals in the population, defined as the proportion of all participants (HIV-negative and HIV-positive) with a measured HIV RNA ≥ 150 copies/mL
 - HIV incidence, estimated with a validated multi-assay algorithm (5) measured in HIV-seropositive participants.
- Cost-effectiveness of the incentive intervention versus control condition using the primary and secondary outcome measures, for example, the cost per additional cohort

participant with viral suppression.

13.3 Study Objectives and Hypotheses

We hypothesize that non-cash HIV care incentives will improve rates of survival with viral suppression in PWID and MSM in India. Providing incentives for achieving verifiable HIV care benchmarks is a demand-stimulation approach, in contrast to supply-focused approaches, such as efforts to increase accessibility or reduce barriers to services. In prior work, we found that a supply-focused intervention – ICCs - was popular and associated with increased HIV testing rates, but did not have a discernible effect on the HIV care continuum. In a pilot trial, we found that treatment incentives were associated with increased access of HIV care and initiation of ART (3). Our objectives for the current trial are as follows:

Primary Objective

To determine if HIV care incentives increase survival with viral suppression at 12 months among HIV-positive PWID and MSM, compared with the control condition.

Secondary Objectives

- To determine if HIV care incentives increase survival with viral suppression at 6, 18, and 24 months among HIV-positive PWID and MSM, compared with the control condition.
- To determine if HIV care incentives increase the proportion with at least one suppressed viral load during study follow-up among HIV-positive PWID and MSM, compared with the control condition.
- To determine if HIV care incentives increase other indices of the care continuum among HIV-positive PWID and MSM, compared with the control condition, including:
 - Time to ART initiation (among those ART-naïve at baseline)
 - Retention to HIV care during follow-up
 - ART medication possession ratio
- To determine if HIV care incentives reduce mortality among HIV-positive PWID and MSM, compared with the control condition.

Exploratory Objectives

- To determine if offering HIV care incentives at ICCs increases:
 - HIV testing rates at ICCs
 - Rates of identifying out-of-care HIV-positive persons at ICCs
- To determine whether treatment incentives are acceptable to participant and providers.
- To determine whether treatment incentives affect community-level indicators of engagement across the HIV care continuum including:
 - Recent HIV testing (among HIV-negative and unknown HIV-positives)
 - Awareness of status (among HIV-positive)
 - Recent visit with HIV medical provider (among HIV-positive)

- Current use of ART (among HIV-positive)
- HIV RNA suppression (among HIV-positive)
- Prevalence of viremic individuals in the population
- HIV incidence estimated by multi-assay algorithm
- To assess the incremental cost-effectiveness ratio of providing HIV care incentives for PWID and MSM, compared with the control condition.

